4.2.2 Secondary Aim

To test the hypotheses of the Secondary Aim, univariate analyses will be used to explore associations between 3-month fracture healing and 3 assessments of serum 25(OH)D

levels: enrolment, 3 months, and change in levels between enrolment and 3 months. Significance will be set at $\alpha=0.20$. Additional descriptive analyses will be performed for serum 25(OH)D at each time point (**Table 3**).

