3.4 Randomization Methods

Each participant will be randomized to 1 of 4 treatment groups: 1) 150,000 IU loading dose vitamin D₃ plus daily dose placebo; 2) loading dose placebo plus 4,000 IU vitamin D₃ per day; 3) loading dose placebo plus 600 IU vitamin D₃ per day; or 4) loading dose placebo plus daily dose placebo. The daily vitamin D₃ supplements/placebo will be provided in a blinded manner. The daily treatment will commence within 1 week of injury and will be taken for 3 months. The loading dose vitamin D₃ supplements/placebo will be given within 1 week of injury and at 6 weeks (+/- 2 weeks) post-injury.

Allocation to the 4 study groups will be concealed using a centralized 24-hour computerized randomization system that will allow internet-based allocation. The treatment allocation will be stratified on the following prognostic factors to ensure balance between the intervention groups: fracture type (closed vs. open) and long bone fracture (tibia vs. femur).

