To determine the effect of low amounts of vitamin D₃ supplementation on fracture healing at 3 months	Low daily dose will increase healing compared to placebo. While the low daily dose is not expected to increase circulating vitamin D as rapidly as the high dose strategies, this comparison will determine if rapid serum increases are necessary to improve fracture healing.	1. FIXIT (Clinical)	Comparisons between the low daily dose & placebo groups will be made using an Independent t-test (alpha=0.20)*
		2. RUST (Radiographic)	
		3. PINP (Biologic)	
		4. CTX (Biologic)	

*Using Phase II screening trial approach, comparisons are non-definitive and an increased alpha level has been adopted.

Table 3: Secondary Outcome Analysis

Objective	Hypothesis	Fracture Healing Outcome	Method of Analysis
To determine if 25(OH)D serum levels are associated with fracture healing at 3 months	There will be an association between fracture healing and: 1) patients' enrolment serum 25(OH)D, 2) their change in 25(OH)D from enrolment to 3 months, 3) their 25(OH)D level at 3 months	1. FIXIT (Clinical)	Associations will be quantified using Univariate Analysis (alpha=0.20)*.
		2. RUST (Radiographic)	
		3. PINP (Biologic)	
		4. CTX (Biologic)	

*Using Phase II screening trial approach, comparisons are non-definitive and an increased alpha level has been adopted.

[figure not shown]
[figure not shown]
[figure not shown]
Table 4: Other Secondary Outcomes Analysis

Objective	Hypothesis	Outcome	Method of Analysis
Supplementation adherence	Daily vitamin D ₃ adherence will be <80% and loading dose vitamin D ₃ adherence will be >95%	Self-report	Summary statistics of means and confidence interval.
		Count of pills	
Participant safety	Adverse events will be rare across all 4 treatment groups.	Adverse event	Summary statistics of proportions.
	Re-operations for a composite of fracture healing complications will follow the same 3 hypotheses as fracture healing.	Re-operations for a composite of fracture healing complications	Summary statistics of proportions.
	Levels of serum calcium will be similar across the 4 treatment groups. Levels of serum calcium will be within normal reference ranges.	Serum Calcium	Summary statistics of means and confidence interval.
	Levels of serum PTH will be similar across the 4 treatment groups. Levels of serum PTH will be within normal reference ranges.	Serum PTH	Summary statistics of means and confidence interval.

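### The planned univariate associations of 3-month and change-in 25(OH)D with healing cannot be told apart from the randomised dose contrast; an arm-adjusted estimate should stand beside them

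*Combined protocol and SAP*

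**What the plan says.** Section 4.2.2 describes the secondary analysis in one sentence: "univariate analyses will be used to explore associations between 3-month fracture healing and 3 assessments of serum 25(OH)D", the three being "levels: enrolment, 3 months, and change in levels between enrolment and 3 months". Significance is set at 0.20. Table 3 gives the hypothesis ("There will be an association between fracture healing and: 1) patients' enrolment serum 25(OH)D", then the change, then the 3-month level) and four healing measures: FIX-IT, RUST, PINP and CTX. That makes 3 × 4 = 12 associations. The method column again names univariate analysis at 0.20, and the footnote reads "Using Phase II screening trial approach, comparisons are non-definitive and an increased alpha level has been adopted".

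Neither place mentions treatment arm, a split by arm, or any covariate. Section 3.4, however, says that allocation is "stratified on the following prognostic factors", namely open versus closed fracture and tibia versus femur.

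Three other sections bear on the point. Section 3.5.2 says that the high-dose arms are meant to raise serum 25(OH)D quickly and that the low-dose arm is not expected to do so as fast. Section 2.4 hypothesises that healing differs between the arms. Section 4.1 sizes the trial on a 2-point FIX-IT gain in the high-dose groups.

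**The concern.** A one-predictor analysis of all participants, with no split by arm, is a pooled analysis on its plain reading, although the plan does not use that word. After treatment starts, a participant's 25(OH)D has two sources: the allocated dose, and differences between people within an arm (adherence, injury, bone and so on). The first source is the randomised contrast that the three primary hypotheses already test. The second is not randomised. A univariate association adds the two together and cannot say how much comes from each.

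If supplementation improves healing as hypothesised, the 3-month and change associations will tend to be positive even if, among people given the same dose, serum level says nothing about healing. The secondary aim would then look like a second line of evidence when it is largely the first one again. This concerns 2 of the 3 exposures, so 8 of the 12 associations. Enrolment 25(OH)D precedes treatment and is independent of arm in expectation.

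Leaving out the stratification factors is a smaller matter of the same kind. Section 3.7.1 expects 1-year union of about 95% for femur and 75% for tibia, so bone is clearly related to healing, and within an arm nothing balances it against 25(OH)D.

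**Working it through.** **1. The plan's own sample size.** Inputs from Section 4.1: difference 2, SD 3, alpha 0.20, power 80%, 10% loss.

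n per group = 2 × (1.282 + 0.842)² × (3/2)² = 20.3, so 21. Then 21/0.9 = 23.3, so 24, and 4 × 24 = 96. The plan's figures reproduce with a two-sided test; a one-sided test would need only 13. The plan gives no sample size or detectable correlation for the secondary aim. I use 4 × 21 = 84 evaluable participants.

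**2. Correlation produced by arm means alone.** Assumptions:
- FIX-IT mean 10 in both high-dose arms and 8 in the other two, SD 3 (Section 4.1).
- 25(OH)D higher by d in the high-dose arms, within-arm SD 10 ng/mL. These values are mine; the documents give none.
- No association between 25(OH)D and healing within any arm.

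With equal arms, the between-arm deviations are ±1 for FIX-IT and ±d/2 for 25(OH)D. So:
- covariance = d/2
- variance of FIX-IT = 9 + 1 = 10
- variance of 25(OH)D = 100 + d²/4
- pooled r = (d/2) / √[10 × (100 + d²/4)]

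For d = 10: 5/√(10 × 125) = 0.14. The table adds results from 10,000 simulated trials per row, 21 per arm, two-sided alpha 0.20.

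| d (ng/mL) | pooled r | pooled test significant | significant with arm in model |
|---|---|---|---|
| 0 | 0.00 | 20% | 19% |
| 5 | 0.08 | 31% | 20% |
| 10 | 0.14 | 51% | 20% |
| 15 | 0.19 | 70% | 20% |
| 20 | 0.22 | 79% | 20% |
| 30 | 0.26 | 89% | 19% |

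Two controls show where the excess comes from. With d = 0, the situation of enrolment 25(OH)D, the pooled test stays at 20%. With d = 20 but no treatment effect on healing, it also stays at 20%. Both separations are needed.

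The standardised effect of 2/3 is the same for RUST (2 points, SD 3) and for the bone markers (20%, SD 30%), so the same correlations follow for them under the same assumptions.

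**3. Uneven means, and the cost of adjusting.** Take assumed 3-month means of 20, 25, 38 and 35 ng/mL for placebo, low daily, high daily and loading. The mean is 29.5 and the between-arm variance is (90.25 + 20.25 + 72.25 + 30.25)/4 = 53.25. The covariance with FIX-IT is (9.5 + 4.5 + 8.5 + 5.5)/4 = 7, so pooled r = 7/√(153.25 × 10) = 0.18. Simulation finds it significant in about 65% of trials, and in 20% within arm.

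Arm explains 53.25/153.25 = 35% of the 25(OH)D variance, so the SE of the slope grows by 1/√0.65 = 1.24. In the two-level setting the factor is √(1 + d²/400): 1.03 at d = 5, 1.12 at 10, 1.41 at 20 and 1.80 at 30. These factors count only the lost spread; the smaller residual variance with arm in the model offsets a little of it.

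**4. Alpha is a separate matter.** The critical |r| at n = 84 is t/√(82 + t²) with t the 0.90 quantile on 82 df, which is 0.141 (2.0% of variance). With arm in the model the critical partial r is 0.144, so adjustment barely moves the threshold. Nor does a smaller alpha deal with the arm contrast: in the uneven-means illustration the pooled test at 0.05 is still significant in 38% of trials, against 5% nominal.

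**The case against.** The best defence is that the aim is association and nothing more. Sections 2.2, 2.4 and 4.2.2 speak of association or correlation, all outcome analyses are declared exploratory, and no passage promises causal or independent evidence. If vitamin D acts through serum level, the pooled association lies on the causal path and is not spurious. This stands, and it is why the univariate correlation should be kept. It does not remove the need to show how much of that correlation is the dose contrast.

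A second defence is that adjusting for arm discards the randomised part of the exposure and keeps the part open to confounding by adherence and injury. That is also correct. The within-arm slope is a companion estimate, not a cleaner causal answer.

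Third, a reader might infer that alpha 0.20 is itself a fault here, because it flags correlations as small as 0.14 and because 12 tests would give 12 × 0.20 = 2.4 expected false positives if every null were true. The documents do not support calling this an error. The level is declared, unadjusted testing is declared, and the trade is a real one: at n = 84, power for r = 0.20 is 71% at alpha 0.20 and 45% at 0.05. Tolerating false positives to avoid misses is a legitimate choice in a screening trial.

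**Conclusion.** The point holds for the 3-month level and the change from enrolment. As written, these associations cannot be separated from the randomised comparisons. The direction follows from the plan's own design: arms meant to differ in 25(OH)D and hypothesised to differ in healing. The size does not, because it depends on 25(OH)D values that the documents do not give. Under the stated assumptions the pooled test is significant in about 31% to 89% of trials, against about 20% with arm in the model. The simulation adjusted for arm only, not for bone or fracture type.

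Three stronger readings should be resisted:
- **The percentages are not error rates.** The marginal association exists in those scenarios, and the test detects it.
- **The problem does not reach enrolment 25(OH)D.**
- **The pooled association does not simply repeat the first hypothesis.** That hypothesis compares the high-dose arms with low dose only, whereas the pooled correlation also includes placebo and so mixes the contrasts.

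Nothing here touches the primary analysis or the sample size. It is a cheap improvement in what an exploratory aim can tell the reader.

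**What to change.** In Section 4.2.2 and Table 3:

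- Keep the univariate correlation for all 12 pairs.
- Add, for each healing measure, a linear model on 25(OH)D with arm, bone (tibia/femur) and fracture type (open/closed). For enrolment 25(OH)D the arm term is optional.
- Report the within-arm slope with a 95% CI beside the correlation.
- State that the between-arm part of the correlation reflects the randomised treatment contrasts, and that the within-arm slope is observational.
- Keep the declared exploratory alpha of 0.20, and rest the interpretation on estimates and intervals, not on which tests cross the threshold.

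This needs no new data: arm, bone and fracture type are known from randomisation. The cost is SAP wording, one extra model per association, and a wider interval for the slope. The SE is about 1.24 times larger in the uneven-means illustration, less if the arms separate 25(OH)D weakly and more if they separate it strongly.

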4.2.3 Other Secondary Outcomes

All other secondary outcomes will be presented using point estimates and appropriate measures of variance to describe supplementation adherence, participant safety, and key aspects of participant compliance with the protocol (**Table 4**). Supplement adherence will be summarized using means and 95% confidence intervals for participant self-reporting and the mean cumulative dose taken at 3 months. The incidence of AEs and re-operations for fracture healing complications in each group will be described with counts and proportions. Serum levels of calcium and PTH will be summarized using means and 95% CIs. Participant compliance with the protocol will be summarized descriptively with counts and proportions.

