Treatment Groups and Study Products	Each participant will be randomized to 1 of 4 treatment groups: 1) 150,000 IU loading dose vitamin D ₃ plus daily dose placebo; 2) loading dose placebo plus 4,000 IU vitamin D ₃ per day; 3) loading dose placebo plus 600 IU vitamin D ₃ per day; or 4) loading dose placebo plus daily dose placebo. All doses of vitamin D ₃ supplements/placebo will be provided in a blinded manner. The daily treatment will commence within 1 week of injury and will be taken for 3 months. The loading dose vitamin D ₃ supplements/placebo will be given within 1 week of injury and at 6 weeks post-injury. All doses of vitamin D ₃ and the placebo will be obtained from Bio-Tech Pharmacal, Inc. (Fayetteville, AK).
Length of Follow-Up	The primary outcome will be assessed at 3 months post-fracture. Participants will be followed for 12 months.

Study Outcomes
	
Fracture healing (primary outcome) will be assessed as follows: 1) clinical fracture healing will be measured using the Function IndeX for Trauma (FIX-IT), 2) radiographic fracture healing will be measured using the Radiographic Union Score for Tibial fractures (RUST), and 3) biological fracture healing will be measured using serum levels of cross-linked C-terminal telopeptides of type I collagen (CTX) and amino-terminal procollagen propeptides of collagen type I (PINP).
 
The secondary outcome will be assessed by measuring 25(OH)D serum levels. Correlations will be assessed between participants' 25(OH)D levels at enrolment, changes in 25(OH)D levels from enrolment to 3 months, and 25(OH)D levels at 3 months and fracture healing as described above.
 
The other secondary outcomes will include assessing supplementation adherence between daily and loading doses, confirming participant safety as measured by adverse events (AEs) and serum levels of calcium and parathyroid hormone (PTH), and assessing protocol adherence (e.g. completion of outcome assessment and participant follow-up).

Sample Size
	
96 patients will be included.

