3.7.4 Data collection and participant follow-up

Upon providing informed consent, baseline demographics will be collected from the patient and from their medical chart (**Table 1**). This includes demographic, medical history, pre-operative blood work-up details (e.g. kidney and liver function tests, calcium, phosphate, and albumin), injury details, fracture characteristics, details on the surgical management of their fracture, and rehabilitation details. Participants will have blood drawn within the fracture clinic that will be analyzed for calcium levels and for CTX, PINP, 25(OH)D, and

PTH (See Section 3.7.5). Post-operative x-rays will be taken as per standard of care (See Section 3.7.6).

Participants will be followed at standard clinical visit intervals for 12 months post-injury including 6 weeks, 3 months, 6 months, 9 months, and 12 months. The Schedule of Events (**Table 1**) details the requirements and procedures for each visit. Participants will have blood drawn within the fracture clinic that will be analyzed for calcium, CTX, PINP, 25(OH)D, and PTH serum levels at 6 weeks and 3 months (See Section 3.7.5). Post-operative x-rays will be taken as per standard of care at each follow-up visit (See Section 3.7.6). Participants will be assessed clinically for FIX-IT at each visit. All study outcomes (as defined above) will be documented on the case report forms (CRFs) at each follow-up visit. A 12-month follow-up was selected because is a standard follow-up period for patients with tibial and femoral shaft fractures and it is a commonly used follow-up period for similar fracture trials.^{7,38} In addition, it is a commonly referenced time period for fracture healing complications requiring reoperation, and will further inform decisions surrounding the larger, definitive phase III RCT.

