6.5 Adverse Event Reporting and Definitions

6.5.1 Adverse event

An AE is any symptom, sign, illness, or experience that develops or worsens in severity during the course of this study.

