6.6 Dissemination Policy

Results from the study will be submitted for publication regardless of whether or not there are significant findings. Every attempt will be made to ensure that the amount of time between completion of data collection and release of study findings are minimized.

Table 1: Schedule of Events

Assessment	Visit 1: Screening & Baseline	Visit 2: 6 Weeks	Visit 3: 3 Months	Visit 4: 6 Months	Visit 5: 9 Months	Visit 6: 12 Months
Screening	•					
Serum Calcium Analysis	•*	•	•			
Informed Consent	•					
Randomization	•					
Collection of Baseline Data (Demographic, Serum Metabolic Panel, Fracture, & Surgical Data)	•					
Nutritional/Placebo Supplementation**	•	•	•			
Assessment of Clinical Fracture Healing (FIX-IT)		•	•	•	•	•
X-Rays of Tibia or Femur	•	•	•	•	•	•
Assessment of Radiographic Fracture Healing (RUST)		•	•	•	•	•
Serum Bone Marker Analysis (CTX & PINP)	•	•	•			
Assessment of Adherence to Supplementation		•	•			
Laboratory Serum 25(OH)D Analysis	•	•	•			
Assessment for AEs		•	•	•	•	•
Serum PTH Level Analysis	•	•	•			
Assessment of Fracture Healing Complications		•	•	•	•	•
*To be assessed as eligibility criteria **Must occur within 1 week of fracture						

Table 2: Primary Outcome Analysis

Objective	Hypothesis	Fracture Healing Outcome	Method of Analysis
To determine the effect of vitamin D₃ dose on fracture healing at 3 months	High doses of supplementation (loading or daily) will increase healing compared to low daily dose. Using high doses will rapidly increase the circulating vitamin D available during fracture callus formation.	1. FIXIT (Clinical)	Patients in the high loading dose & high daily dose groups will be combined for a 2:1 comparison against low daily dose group using an Independent t-test (alpha=0.20)*
		2. RUST (Radiographic)	
		3. PINP (Biologic)	
		4. CTX (Biologic)	
To determine the effect of vitamin D₃ frequency on fracture healing at 3 months	High loading dose increases healing compared to high daily dose. Loading doses will overcome medication adherence issues and increase circulating vitamin D even more rapidly than daily doses.	1. FIXIT (Clinical)	Comparisons between the high loading dose & high daily dose groups will be made using an Independent t-test (alpha=0.20)*
		2. RUST (Radiographic)	
		3. PINP (Biologic)	
		4. CTX (Biologic)	

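### AE summaries have no time window, so the natural reading pools about nine off-supplement months with the three on supplement and weakens the between-arm contrast for common events

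*Combined protocol and SAP*

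**What the plan says.** **Summary.** Section 4.2.3 states: "The incidence of AEs and re-operations for fracture healing complications in each group will be described with counts and proportions". The AE row of Table 4 plans summary proportions and carries the hypothesis that AEs will be rare in all four arms. Neither place gives a time window, an on-treatment or treatment-emergent definition, or a split by period.

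**Exposure.** Section 3.4 says of the capsules: "The daily treatment will commence within 1 week of injury and will be taken for 3 months". The loading doses are "given within 1 week of injury and at 6 weeks (+/- 2 weeks) post-injury".

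**AE collection.** Section 6.5.1 defines an AE as "any symptom, sign, illness, or experience that develops or worsens in severity during the course of this study", and Section 3.7.3 uses the same definition. Section 3.7.4 says "Participants will be followed at standard clinical visit intervals for 12 months post-injury". The Table 1 row "Assessment for AEs" is marked at 6 weeks and at 3, 6, 9 and 12 months.

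**What counts as an AE.** Section 3.7.3 identifies fracture-healing complications from among the AEs. Delayed union is judged against a 4-month median healing time, and nonunion requires at least 6 months from fracture.

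**Data available.** Section 3.7.4 says that study outcomes "will be documented on the case report forms (CRFs) at each follow-up visit".

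**The concern.** All arms take capsules for 3 months, and the second loading dose falls at about 6 weeks, yet AE collection runs for 12 months. If each arm gets an AE proportion over all follow-up, a participant whose only event occurs in month 9 counts the same as one whose event occurs on supplement. Later events that are equally common in all arms add to every proportion and pull the arms together.

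The late events are partly built into the definitions, since delayed union and nonunion cannot be diagnosed by month 3. Table 4 also expects re-operations for healing complications to follow the healing hypotheses, which would mean fewer at higher doses. If the complications themselves moved that way, a late benefit could offset an early excess of other events within a single AE figure.

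The Introduction names dosing safety in this population as something research must establish, and Section 3.5.4 commits to watching for falls. Falls can happen at any time in the year, and the laboratory measures do not capture them.

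**Working it through.** **Inputs from the documents.** Supplementation lasts 3 months (Section 3.4), AEs are assessed to 12 months (Table 1), and there are 24 participants per arm (Section 4.1). No AE rate by arm or period is given, so every AE rate below is an assumption.

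**The plan's own figure.** There is none for AEs. The only size calculation is for healing, and it reproduces: 2 × (1.2816 + 0.8416)² × 3² / 2² = 20.3, rounded up to 21; 21 / 0.90 = 23.3, rounded up to 24; 4 × 24 = 96. Here it only fixes the arm size.

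**Model.** Let p0 and p1 be the risks of at least one AE in months 0-3 in the control and active arms. Let L be the risk of at least one AE in months 3-12, taken as equal in both arms and independent of earlier events. Then:

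- 12-month risk = 1 − (1 − p)(1 − L)
- 12-month risk difference = (p1 − p0)(1 − L)

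The absolute excess therefore shrinks by the factor 1 − L, and the risk ratio shrinks further because the control risk rises.

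**Results** (ratios from unrounded values)

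| Assumed background | 1 − L | Months 0-3 | 12 months | Risk difference | Risk ratio |
|---|---|---|---|---|---|
| 10% per quarter, constant | 0.90³ = 0.729 | 10% vs 20% | 34.4% vs 41.7% | 0.10 to 0.073 | 2.0 to 1.21 |
| 10% in months 0-3, then 2% per quarter | 0.98³ = 0.941 | 10% vs 20% | 15.3% vs 24.7% | 0.10 to 0.094 | 2.0 to 1.62 |
| 5% per quarter, constant | 0.95³ = 0.857 | 5% vs 10% | 18.5% vs 22.8% | 0.05 to 0.043 | 2.0 to 1.23 |
| 15% per quarter, constant | 0.85³ = 0.614 | 15% vs 30% | 47.8% vs 57.0% | 0.15 to 0.092 | 2.0 to 1.19 |
| 0.5% per quarter, 20% added harm in months 0-3 | 0.995³ = 0.985 | 0.5% vs 20.4% | 2.0% vs 21.6% | 0.199 to 0.196 | 40.8 to 10.9 |

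For the first row, the control risk is 1 − 0.90 × 0.729 = 0.344 and the active risk is 1 − 0.80 × 0.729 = 0.417. For the second, they are 1 − 0.90 × 0.941 = 0.153 and 1 − 0.80 × 0.941 = 0.247.

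**A check tied to a document figure.** Section 3.7.1 expects 1-year union of about 95% (femur) and 75% (tibia). As a rough proxy, count only fractures not united at 1 year as late AEs, equally in both arms, so that L is 0.05 or 0.25. With 10% versus 20% in months 0-3:

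- Femur: 1 − 0.90 × 0.95 = 14.5% versus 1 − 0.80 × 0.95 = 24.0%; risk ratio 1.66, risk difference 0.095.
- Tibia: 1 − 0.90 × 0.75 = 32.5% versus 1 − 0.80 × 0.75 = 40.0%; risk ratio 1.23, risk difference 0.075.

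These fall in the same range as the first two rows of the table.

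**The case against.** **The plan does not say 12 months.** A reader might infer that the plan commits to one 12-month proportion per arm. It does not: Section 4.2.3 is silent on the window and promises counts as well as proportions. Visit-level recording would let the analyst tabulate months 0-3. This stands, so the defect is an unstated window. Even so, the whole-study AE definition and the pairing with re-operations in the same sentence make full follow-up the natural reading.

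**The named harm is protected.** A reader might also infer that any supplement-related harm would be hidden. Hypercalcemia is the first harm that Section 3.5.4 discusses. Calcium and PTH are measured only at enrolment, 6 weeks and 3 months and are summarised separately. SAEs, unanticipated problems and serious unexpected reactions are also reported individually. This stands.

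**Splitting by event type helps.** It is tempting to say that dilution survives any split by type. For a type with near-zero background it hardly does: the risk difference goes from 0.199 to 0.196. The dilution matters for overall AEs and for types with appreciable background.

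**The size rests on assumptions.** Constant background risk for a year after trauma surgery has no support in the documents, and Table 4 expects AEs to be rare. With a front-loaded background most of the contrast survives (1.62, not 1.21). The risk ratio also shows more loss than the risk difference, which keeps 61% to 94% of its value across the first four table rows. This stands as a limit on size. The direction holds as long as later background is similar in the arms.

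**Little rides on it.** The AE analysis is descriptive. With 24 per arm, 10% versus 20% is about 2 versus 5 participants, which is weak evidence in either window. True, but the remedy costs very little.

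**Conclusion.** The point holds as a gap in the AE summary: no window is stated, and the default pools about nine off-supplement months with three on supplement. The result is a weaker contrast for overall AEs and for event types with appreciable background. For an assumed 10% versus 20% in months 0-3, the 12-month risk ratio is about 1.2 under a constant 10% background per quarter and about 1.6 if later background is 2% per quarter. The risk difference falls from 0.10 to 0.07 and to 0.094 respectively. These figures assume equal later risk in the arms and independence between periods. They are illustrations, because the documents give no AE rates.

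A reader might conclude that the safety comparison will be falsely reassuring. The documents do not support that: calcium and PTH are confined to the supplementation period, rare specific harms barely dilute, and the pooled summary is inferred. The analysis is descriptive, and neither the primary analysis nor the sample size is touched. This is a modest, inexpensive improvement to the safety reporting.

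**What to change.** In Section 4.2.3 and the AE row of Table 4, state the window and report AEs and SAEs per arm, as participants with an event and as number of events, for:

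1. first dose to the 3-month visit;
2. the 3-month visit to 12 months;
3. the whole 12 months, as an overall summary.

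Assign each event to a period by its onset date or, if that is not recorded, by the visit at which it was recorded. The CRF is not among the documents, so whether it already holds an onset date cannot be judged. Keep re-operations and fracture-healing complications on the 12-month window, since delayed union and nonunion cannot be assessed by month 3.

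The cost is an additional table column or two and sparse counts within each period. Delayed effects of the supplements would fall in the second period, which is still reported, so nothing is lost. The visit schedule and the descriptive status of the analysis stay as they are. Fixing the periods now also avoids choosing a window after unblinding.
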